1. BACKGROUND AND RATIONALE

The 5-year survival for Head and Neck squamous cell carcinoma (HNSCC) across all TNM stage groups is approximately 50% [1]. Patients who are present with stage I & II disease have significantly better survival. When a patient presents to their general practitioner (GP) with symptoms suggestive of HNSCC, they may be referred for urgent specialist input through the suspected cancer referral (SCR) pathway, which include dedicated neck lump clinics. Majority of the patients diagnosed via the SCR pathway present with Stage III & IV disease, which has a direct impact on outcomes.

HNSCC is classified as an uncommon cancer and as such diagnosis and treatment is undertaken in specialist tertiary referral centres. The care of patients initially diagnosed with HNSCC in smaller secondary care hospitals is transferred to these specialist tertiary referral centres via the Inter Trust Transfer (ITT). ITT can introduce delays in treatment pathways resulting in a failure to achieve cancer treatment targets. Southwest London HNSCC diagnostic pathway review which was undertaken in February 2021 demonstrated that 40% of ITTs received were greater than 38 days after referral and that 68% of the 62 day target breaches were in patients with ITT.

HNSCC is known to shed fragments of DNA, called circulating tumor DNA (ctDNA) into the bloodstream [2]. We have developed novel ultra-sensitive (>90% sensitivity) next generation sequencing (NGS) assay for circulating HPV DNA [3] in patients with non-metastatic locally advanced head and neck cancer. Our current work involves ctDNA detection to cover the spectrum of genetic alterations in HNC using a single sequencing workflow to detect copy number aberrations (CNAs), HPV DNA (to cover 99.9% of HNC related HPV) and somatic mutations.

The use of ultra-sensitive NGS assay for detection of ctDNA using a simple blood test (liquid biopsy) holds a great promise for cancer screening and early diagnosis and can lead to better survival results and less disease burden. This has been proven in proof of principle studies in nasopharyngeal cancer [4] (Chan N Engl J Med 2017; 377:513-522). Furthermore, this test can be administered in smaller secondary care hospitals in parallel to the ITT. With a quicker turnaround (1-2 weeks), the liquid biopsy can help expedite the patient journey through the cancer pathways reducing the incidence of cancer target breaches. In order to design studies to test this hypothesis we require preliminary data quantifying sensitivity and specificity of our assay in this setting.

2. STUDY OBJECTIVES

2.1 Hypothesis

The NGS assay has a high sensitivity and specificity for detection of ctDNA in early HNSCC

2.2 Aims

To test the feasibility of the NGS assay for detection of ctDNA in patients with early HNSCC

3. STUDY SETTING

3.1 Study Design

This is a prospective observational sample collection study in patients referred to neck lump clinics via the SCR.

3.2 End Points

- Primary endpoint – Measure the sensitivity of the NGS assay for detection of ctDNA at baseline in patients with early HNSCC
- Secondary end-point - Measure the specificity of the NGS assay for detection of ctDNA at baseline in patients with early HNSCC

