3.3 Inclusion/ Exclusion Criteria

Inclusion Criteria

- Patients referred for an Ultrasound guided fine needle aspiration (USFNA) in the neck lump clinic.

Exclusion Criteria

- Patient found to have a lump in the thyroid gland at the time of USFNA
- Unable to give informed consent for biological sample collection.
- Unable to safely participate in clinic sample collection

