7. STATISTICS AND DATA ANALYSIS

7.1 Statistical Considerations

This is a pilot study that aims to investigate the feasibility of using HPV DNA as a biomarker of early diagnosis of HNSCC. To this effect, we will focus on identifying the sensitivity of the NGS assay in patients who been diagnosed with invasive cancer. A sensitivity of greater than 70% would be necessary for further investigation in a larger study. We hope to recruit 49 patients who undergo USFNA and are diagnosed with HNSCC and a further 121 patients who undergo USFNA and do not have invasive HNSCC. The standard ctDNA test will be compared against the tissue diagnosis of invasive cancer as per the tumour biopsy.

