7.2 Sample Size

Assuming disease prevalence at baseline of 99%, if ctDNA is detectable in at least 39 out of 49 patients, this will enable us to demonstrate a sensitivity of at least 70% (i.e. rule out the maximum futility proportion), and assume a true sensitivity of 85% (the minimum efficacy proportion), with 80% power and a one-sided type I error of 0.05.”

If ctDNA is undetectable in at least 112 out of 121 patients, this will enable us to demonstrate a specificity of at least 85% (i.e. rule out the maximum futility proportion), and assume a true specificity of 95% (the minimum efficacy proportion), with 90% power and a one-sided type I error of 0.01 (Single stage phase II A'Hern design, software used nQuery v8.7.2).

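### The endpoints are stated for undefined 'early' HNSCC but the analysis uses invasive HNSCC of any stage, and the specificity endpoint names patients who have the disease

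*Combined protocol and SAP*

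**What the plan says.** Three sections of the combined protocol and SAP name an 'early' population:

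- Section 2.1, hypothesis: "The NGS assay has a high sensitivity and specificity for detection of ctDNA in early HNSCC".
- Section 2.2, aim: "To test the feasibility of the NGS assay for detection of ctDNA in patients with early HNSCC".
- Section 3.2, endpoints: the primary is "Measure the sensitivity of the NGS assay for detection of ctDNA at baseline in patients with early HNSCC" and the secondary is "Measure the specificity of the NGS assay for detection of ctDNA at baseline in patients with early HNSCC".

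No section defines the term. The sections that decide who is enrolled and what is computed set no stage limit:

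- Section 3.3 admits "Patients referred for an Ultrasound guided fine needle aspiration (USFNA) in the neck lump clinic". Its exclusions concern thyroid lumps, consent and safe participation.
- Section 7.1 looks at sensitivity in patients diagnosed with invasive cancer and sets the condition for going on: "A sensitivity of greater than 70% would be necessary for further investigation in a larger study".
- Section 7.2 gives the rule "if ctDNA is detectable in at least 39 out of 49 patients".
- Section 7.3 puts all participants with invasive HNSCC in the denominator of sensitivity.
- Section 7.4 triggers the primary analysis at 49 patients with invasive HNSCC and the secondary analysis at 121 patients without it.

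Section 1 separates stage I-II, with its better survival, from stage III-IV, and says that most patients diagnosed through the suspected cancer referral (SCR) pathway are in the later group. Section 7.1 also describes the marker as a "biomarker of early diagnosis of HNSCC", which is a different use of the word 'early'.

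**The concern.** The quantity to be computed is clear. What it is called is not. Section 1 itself contrasts stage I-II with stage III-IV, so a reader of section 3.2 may well take 'early HNSCC' to mean stage I-II. By the protocol's own account, most of the 49 cancers would then lie outside the population named in the primary endpoint.

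The study exists to supply preliminary figures for a later design, and sensitivity above 70% is the stated condition for that step. A pooled any-stage figure reported under the section 3.2 label would be read as performance in early disease and could misinform the next study.

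The secondary endpoint raises a simpler problem: it places specificity in patients who have the disease.

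**Working it through.** **1. The sections side by side**

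| Item | Section | Population |
|---|---|---|
| Hypothesis, aim | 2.1, 2.2 | early HNSCC, undefined |
| Primary endpoint | 3.2 | early HNSCC, undefined |
| Secondary endpoint | 3.2 | early HNSCC, undefined |
| Eligibility | 3.3 | referred for USFNA, no stage criterion |
| 70% criterion | 7.1 | diagnosed invasive cancer |
| 39-of-49 rule | 7.2 | no stage restriction |
| Sensitivity definition | 7.3 | invasive HNSCC |
| Primary analysis trigger | 7.4 | 49 with invasive HNSCC |
| Specificity sample | 7.1, 7.2, 7.4 | 121 without invasive HNSCC |

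The first three rows disagree with the rest. 'Any stage' is my inference from the absence of a limit; the protocol's own term is invasive HNSCC.

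**2. The plan's own rule**

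Inputs from section 7.2: n = 49, cut-off 39, null sensitivity 0.70, alternative 0.85, one-sided error 0.05, power 80%. With exact binomial tails:

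- Cut-off 39: P(X ≥ 39 | 49, 0.70) = 0.092 and P(X ≥ 39 | 49, 0.85) = 0.893.
- Cut-off 40: P(X ≥ 40 | 49, 0.70) = 0.048 and P(X ≥ 40 | 49, 0.85) = 0.809.

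So 49 reproduces as the sample size, but with cut-off 40. That is a separate matter. Both cut-offs are carried below to show that it does not affect this point.

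**3. What a pooled pass permits in stage I-II**

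The rule allows 49 − 39 = 10 misses (49 − 40 = 9 at cut-off 40). Let e be the number of stage I-II cases among the 49. If every stage III-IV case is detected and all misses fall in stage I-II, the smallest number of stage I-II detections compatible with a pass is max(0, e − 10), or max(0, e − 9) at cut-off 40.

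A majority of 49 is at least 25, so if the sample follows the statement in section 1, e is at most 24. The documents give no exact share. The smaller values of e are assumptions.

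| Stage I-II share | e | Minimum at 39/49 | Minimum at 40/49 |
|---|---|---|---|
| largest consistent with 'majority' | 24 | 14/24 = 58% | 15/24 = 62.5% |
| 40% (assumed) | 20 | 10/20 = 50% | 11/20 = 55% |
| 30% (assumed) | 15 | 5/15 = 33% | 6/15 = 40% |
| 20% (assumed) | 10 | 0/10 | 1/10 |

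The Clopper-Pearson 95% interval is 0.37-0.78 for 14/24 and 0.41-0.81 for 15/24. The first row is the mildest of these limits, because fewer stage I-II cases leave more room for misses among them.

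**4. What the sample could say about stage I-II**

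An exact one-sided 0.05 test of 70% against 85% in stage I-II alone needs 21/24 (power 0.51) or 14/15 (power 0.32). Good results below those cut-offs would not exclude 70%: 20/24 has a 95% interval of 0.63-0.95, and 13/15 has 0.60-0.98.

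**5. Specificity**

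Specificity is the proportion of people without the disease who test negative. In patients with HNSCC, early or not, its denominator is empty. Sections 7.1, 7.2 and 7.4 use the 121 patients without invasive HNSCC, which is a valid denominator.

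**The case against.** The strongest reply is that this is loose wording in a pilot. Sections 7.1 to 7.4 agree with one another, and section 7.3 states the denominator of sensitivity outright. When the authors mean stage they write the stage numbers, as in section 1, and the stated purpose is early diagnosis in this referral setting. On that reading, passing a pooled 70% criterion when pooled sensitivity really exceeds 70% is the right result. Nothing in the sample size or decision rule needs to change.

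Much of this stands. Early diagnosis is the better supported reading, and under it the analysis is coherent. The wording of sections 2.1, 2.2 and 3.2 is then wrong and still needs correcting. The reply does not reach the specificity endpoint, which fails on either reading.

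Three stronger inferences are tempting and are not supported:

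- **That stage is not collected.** Section 5.1 lists broad areas only and refers to an Excel Data Tool that is not part of the documents reviewed. Section 6.2 provides for clinicopathological data.
- **That the assay probably falls below 70% in stage I-II.** The documents give no stage-specific sensitivity and no exact stage mix. Any probability of a misleading pass would rest on assumed values, so none is offered here.
- **That the sponsor meant stage I-II and has designed the wrong study.** The text does not settle the meaning, and it leans the other way.

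**Conclusion.** The point holds as a mismatch between the stated endpoints and the planned analysis, and it should be fixed. It rests on the text alone. Under a stage I-II reading, a pooled pass does not support the primary endpoint and no stage I-II estimate is planned. Under an early-diagnosis reading, the label is wrong. The secondary endpoint is wrong under both.

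The size depends on the stage mix. At the largest stage I-II count consistent with section 1, a pass can coexist with 58% detection in stage I-II, and with lower values if that group is smaller. These limits assume that every stage III-IV case is detected and that the 49 follow the majority statement, which section 1 makes about the referral pathway and not about these two clinics. The conclusion is the same at cut-off 39 or 40. The harm is in how the result would be reported and used; the pooled figure itself remains computable and valid for invasive HNSCC of any stage.

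**What to change.** No extra patients are needed.

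1. The sponsor states what 'early' means and aligns sections 2.1, 2.2 and 3.2 with 7.1-7.4. If early diagnosis is meant, word the primary endpoint as sensitivity in invasive HNSCC of any stage among SCR neck-lump patients referred for USFNA, and state in 7.1 and 7.2 that the 70% criterion applies to the pooled group. If stage I-II is meant, say that the pooled rule does not test it.
2. Reword the secondary endpoint as specificity in participants without invasive HNSCC, matching section 7.2.
3. Confirm that TNM stage is captured in the Excel Data Tool or in the clinicopathological data of section 6.2, or add it. In section 7.3, report descriptive sensitivity for stage I-II and stage III-IV with exact 95% intervals, and let any early-stage statement rest only on the stage I-II estimate.

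The cost is wording, at most one new data field and one table. The headline claim becomes narrower, and the stage I-II estimate will be imprecise, with about 24 patients or fewer. Stage may have to be retrieved from the treating centre, because section 8.1 has data entered at the clinic while section 1 describes transfer of care to tertiary centres.

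Re-sizing for stage I-II is not proposed. Reaching 49 such cases would take 49/0.49 = 100 HNSCC cases at the largest share, or 49/0.30, about 164, at an assumed 30%. At the 30-40 cases a year in section 7.4, that is roughly 2.5 years (100/40) to 5.5 years (164/30).

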3.3 Inclusion/ Exclusion Criteria

Inclusion Criteria

- Patients referred for an Ultrasound guided fine needle aspiration (USFNA) in the neck lump clinic.

Exclusion Criteria

- Patient found to have a lump in the thyroid gland at the time of USFNA
- Unable to give informed consent for biological sample collection.
- Unable to safely participate in clinic sample collection

4. TRIAL PROCEDURES

4.1 Patient Identification and Consent

The proposed observational sample collection study will recruit patients referred to the neck lump clinics via the SCR pathway. Patients are classified as low and high risk in the neck lump clinic following clinical history and examination by the clinician. Patients classified as high risk are

referred for an USFNA. These patients will be approached for screening by a designated study research nurse and be provided with a patient information sheet (PIS). They will be made aware that definite eligibility will be determined following USFNA. Patients will only be eligible if they do not have a lump in their thyroid gland after undergoing USFNA. Following USFNA, eligible patients will be approached by the research nurse to address any concerns and to sign an informed consent.

Blood sample will be collected from patients who sign the informed consent. As per the study procedure, the patient will be consented on the same day i.e. the day of the neck lump clinic, that they receive the consent form. They will be given adequate time to consider consenting to the study and have the opportunity to ask questions.

The blood sample will be transferred to the Biobank at RMH via first class post for processing and storage. These samples will then be transferred in batches to ICR or CMP and analysed for the presence of and to quantify the levels of ctDNA. With advances in technologies for analysis we will also perform a complete genomic analysis.

The study will be run at head and neck lump clinics at Kingston Hospital NHS Foundation Trust and London North West University Healthcare NHS Trust.

4.2 Withdrawal criteria

Patients may withdraw from the study at any time at their own request, or they may be discontinued at the discretion of the Principal Investigator. This can occur for the following reasons:

- Patient decision
- Ineligibility
- PI decision

If the patient is withdrawn from the study, the primary reason as well as the date of withdrawal will be recorded in the in the Excel Data Tool (combined eCRF and database). Should a patient withdraw consent for their samples to be used in the study, the samples will be destroyed. Data collected at the point of withdrawal will continue to be used by the study team.

4.3 Study completion and end of trial definition

The end of study accrual will be when the requisite numbers of patients have been recruited and the last blood sample is taken as per trial protocol.

5. DATA ACQUISITION AND HANDLING

5.1 Clinical data

We will be collecting identifiable data as part of the study. This information will be held by the study sponsor on an excel spreadsheet stored on a Trust computer in line with local data governance policies and GDPR. Each patient enrolled in the study will have a unique study ID generated.

The full dataset is available in an associated Excel Data Tool (combined eCRF and database). The dataset is divided into the following areas:

1. General patient details: Demographics, smoking/alcohol
2. Diagnosis – Histology/cytology from the USFNA

5.2 Samples and Molecular data

Biological specimens will be identified only using the study ID (link-anonymised). As such, no patient identifiable data will be processed outside of RMH.

6. STORAGE AND ANALYSIS OF SAMPLES

6.1 Specimens

A 20ml blood sample (2x 10ml blood collection tube, Streck or other appropriate) for plasma extraction and collection of buffy coat or PBMCs will be taken. The blood will be centrifuged to separate the plasma and buffy coat and then labelled and stored at -80°C.

6.2 Storage, labelling and postage of biological samples

All the samples will be labelled in accordance with good clinical practice and local protocols. If the patient consents to participate in the study, the name of the study, the study ID and the date of acquisition should also be added to the label. Sample storage will be in compliance with the Human Tissue Act (HTA).

The blood sample will be collected by the research nurse that attends the neck lump clinic. They will consent the patient, collect the sample and will arrange for the sample to be transferred to the Biobank. The research nurse will be adequately trained in the correct procedures for sample collection and transfer, ensuring procedures are compliant with the HTA. The blood sample will be transferred to Biobank at RMH via a courier or royal mail special delivery in an approved packaging for processing and storage. They will be link-anonymised and transferred to ICR for

analysis, where samples will be stored in secure facilities. Samples labelled in an anonymised fashion with no identifiable features may be shared with external institutions and collaborators. Biological samples retained for the study will be encoded with a unique identifier and other patient identifiers will be removed prior to storage in order to maintain patient confidentiality.

Laboratory researchers will not have access to any details that identify the patient in almost all circumstances. Certain key individuals within the study team will be able to link the unique identifier with the patient's identification details. This will allow the collection of clinicopathological data to complement the molecular data results from the study.

Extracted nucleic acids will be stored for future analysis in secure facilities at the Institute of Cancer Research. All samples will be held in compliance with the Human Tissue Act (HTA).

The chief investigator will have overall responsibility for the samples and will delegate responsibilities to appropriately trained staff. While the samples are stored at the RMH Biobank, the biobank manager will have overall responsibility for the samples. The scientific officer based at ICR will request the samples to be transferred for analyses. The samples will be tracked at all times. Excess samples which are left over will be transferred back to the biobank and will be stored as per their SOPs, which include transfer to off-site facilities for long term storage.

6.3 Molecular analyses

Nucleic acid extraction

Nucleic acids will be extracted from plasma with buffy coat used for germline nucleic acid sequencing. DNA samples will be subjected to sequencing analysis for identification of ctDNA.

7. STATISTICS AND DATA ANALYSIS

7.1 Statistical Considerations

This is a pilot study that aims to investigate the feasibility of using HPV DNA as a biomarker of early diagnosis of HNSCC. To this effect, we will focus on identifying the sensitivity of the NGS assay in patients who been diagnosed with invasive cancer. A sensitivity of greater than 70% would be necessary for further investigation in a larger study. We hope to recruit 49 patients who undergo USFNA and are diagnosed with HNSCC and a further 121 patients who undergo USFNA and do not have invasive HNSCC. The standard ctDNA test will be compared against the tissue diagnosis of invasive cancer as per the tumour biopsy.

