7.3 Statistical analysis

The statistical analyses will be performed by [name] [name], who is a co-investigator on the project using the R statistical software package. Given, that the study will involve simple statistical analyses, an expert statistician will not be required to perform the analyses. However, we will ask the study statistician to check the analyses for accuracy.

All quantitative data will be analysed for normality and presented accordingly as number of observations, measure of central tendency for HPV DNA copy number and variance. Qualitative data will be presented as a number of observations and percentages

A Chi square test will also be performed to check for the association between plasma ctDNA and the diagnosis of viable invasive HNSCC.

Sensitivity at baseline is defined as the proportion of participants with invasive HNSCC who have ctDNA detected.

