7.4 Study duration

The study will continue until up to 49 patients with invasive HNSCC and 121 patients without invasive SCC, have been recruited. The study will be completed once all 170 patients have been recruited and samples analysed.

The study will be run at the head and neck lump clinics at Kingston Hospital NHS Foundation Trust and London North West University Healthcare NHS Trust. Based on previous year's figures, approximately 200 patients are referred each year for USFNA following assessment in the clinic. Of these, 30-40 patients get diagnosed with HNSCC and 10-15 with Thyroid cancer. Therefore, we anticipate that this study will complete recruitment in 9-12 months.

The primary analysis will be performed once all 49 patients with invasive HNSCC are recruited and samples analysed, whereas the secondary endpoint analysis will be performed once 121 patients without invasive HNSCC have their samples analysed.

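### No section says how disease status is set without a tumour biopsy or after a benign or non-diagnostic aspirate, so an HNSCC missed at USFNA could be counted as a control

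*Combined protocol and SAP*

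**What the plan says.** Section 7.1 names the reference standard: "The standard ctDNA test will be compared against the tissue diagnosis of invasive cancer as per the tumour biopsy". The cases are 49 patients diagnosed with HNSCC. The controls are "a further 121 patients who undergo USFNA and do not have invasive HNSCC".

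Section 5.1 divides the dataset into two areas, and the diagnostic one reads "Histology/cytology from the USFNA". It adds that "The full dataset is available in an associated Excel Data Tool", which is not among the documents reviewed. Section 6.2 lets certain study staff link identifiers, and says of this: "This will allow the collection of clinicopathological data to complement the molecular data results from the study".

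Section 7.3 gives the primary measure: "Sensitivity at baseline is defined as the proportion of participants with invasive HNSCC who have ctDNA detected". It has no matching definition of specificity. It also plans a chi-square test of "the association between plasma ctDNA and the diagnosis of viable invasive HNSCC".

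Section 7.4 sets the timing: "The primary analysis will be performed once all 49 patients with invasive HNSCC are recruited and samples analysed". The secondary analysis follows once samples from 121 patients without invasive HNSCC have been analysed. Eligibility (3.3, 4.1) rests on referral for USFNA and the absence of a thyroid lump; a biopsy is not required.

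**The concern.** Both endpoints are proportions whose denominators are set by disease status, so the rule for assigning status is part of what is being estimated. 7.1 and 5.1 point to different sources, and the term tumour biopsy can be read in two ways:

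- **A biopsy separate from the USFNA.** Participants who never have one then have no stated comparator. Many of the 121 controls may be in this position.
- **Tissue or cells obtained at the USFNA.** 7.1 and 5.1 then agree, but the aspirate is the reference standard and its errors pass into the 2x2 table.

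On either reading, a participant with HNSCC and a benign or non-diagnostic aspirate could be placed among the controls. If ctDNA is detected, a correct assay result is scored as a false positive. The participant also drops out of the sensitivity denominator, so sensitivity would describe only cancers that the aspirate found. With no rule fixed in advance, status could also be revisited after ctDNA results are seen. The study is about early HNSCC, so participants who are ctDNA-positive and aspirate-negative are ones it would particularly want to classify correctly.

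**Working it through.** **Inputs from section 7.2.** Specificity: n = 121, success at 112 or more negatives, p0 = 0.85, p1 = 0.95, one-sided alpha 0.01, power 90%. Sensitivity: n = 49, success at 39 or more positives, p0 = 0.70, p1 = 0.85.

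**Inputs assumed.** m is the number of missed HNSCC counted among the 121 controls, and p is the chance that a missed cancer is ctDNA-positive. The documents give neither. I use m = 0, 1, 2 and p = 0.85 (the design sensitivity) or 0.50. For scale, with 49 cancers found, one missed is 1/50 = 2.0% and two are 2/51 = 3.9% of all enrolled cancers. These are shares of enrolled cancers, not USFNA miss rates.

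**Step 1: reproduce the plan's specificity design.**
P(Bin(121, 0.85) ≥ 112) = 0.0093, within 0.01.
P(Bin(121, 0.95) ≥ 112) = 0.918, above 90%.
The design reproduces.

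**Step 2: specificity with misclassified controls.** With true specificity s, the number of negatives is Bin(121 − m, s) + Bin(m, 1 − p). The chance of at least 112 negatives is:

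| s | p | m = 0 | m = 1 | m = 2 |
|---|---|---|---|---|
| 0.95 | 0.85 | 91.8% | 86.3% | 78.5% |
| 0.95 | 0.50 | 91.8% | 88.7% | 84.9% |
| 0.97 | 0.85 | 99.6% | 99.1% | 97.8% |
| 0.97 | 0.50 | 99.6% | 99.3% | 98.7% |

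Expected apparent specificity is [(121 − m)s + m(1 − p)]/121. For s = 0.95, p = 0.85, m = 2 this is (119 × 0.95 + 2 × 0.15)/121 = 113.35/121 = 93.7%.

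**Step 3: direction.** A missed cancer is negative with probability 1 − p and a true control with probability s. The bias is therefore downward when p > 1 − s and upward when p < 1 − s. Extreme case: at s = 0.85 and p = 0, the chance of passing is 0.0093, 0.0102 and 0.0111 for m = 0, 1, 2, slightly above the stated 0.01 once a cancer is missed. At s = 0.85 and p = 0.85 it falls instead, to 0.0052 and 0.0027 for m = 1 and 2.

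**Step 4: sensitivity.** Hold sensitivity over all cancers, found and missed, at 0.70. Sensitivity among the 49 found is then [0.70(49 + m) − mp]/49. For m = 2, p = 0.50: (35.7 − 1.0)/49 = 0.708. The chance of at least 39 of 49 is:

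| p | m = 0 | m = 1 | m = 2 |
|---|---|---|---|
| 0.50 | 9.2% | 10.3% | 11.4% |
| 0.85 | 9.2% | 8.5% | 7.8% |

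The 9.2% at m = 0 exceeds the planned 5% because of the cut-off of 39 itself. That is a separate matter. Misclassification moves the figure by about one to two points, in either direction.

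**The case against.** **The Data Tool may already hold the answer.** 5.1 lists headings, and the full dataset sits in a file not supplied. 6.2 allows clinicopathological data to be linked. A reader might infer that biopsy or final diagnosis is not collected at all; the documents do not show that. This stands as a limit on the point. But a field in a database is not an analysis rule, and no section says that status is taken from it, or when.

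**The groups are already worded by disease.** 7.1, 7.3 and 7.4 speak of patients with and without invasive HNSCC, not of aspirate results. A reader might infer that 7.4 starts the analyses on recruitment and sample analysis regardless of status. It does not: both triggers name disease groups, so status must be assigned first. Only the method of assigning it is unstated.

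**7.1 and 5.1 may not conflict.** If the biopsy is the tissue taken at USFNA, they agree. That is a fair reading, and the documents do not decide between the two. It leaves the question of aspirates that are non-diagnostic or falsely benign.

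**The bias is not always conservative for specificity.** It is tempting to say that misclassification can only lower the chance of meeting 112 of 121. Step 3 shows that this fails when missed cancers are positive less often than true controls, although the reversal is very small.

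**The size rests on assumptions.** This stands. Larger m gives more striking figures (43.1% at m = 5, s = 0.95, p = 0.85), but nothing in the documents supports a particular miss rate, so a claim that the specificity endpoint is seriously underpowered is not warranted.

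**Conclusion.** The gap in the text is certain: the plan names a biopsy as comparator, lists only the USFNA result, and does not say how status is set when there is no biopsy or the aspirate is benign or non-diagnostic. The consequence is conditional on status being taken from the data listed in 5.1, which no section states.

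Under that condition, and if missed cancers are ctDNA-positive more often than true controls, specificity is understated. At the design value of 95%, one missed cancer that is 85% positive takes the chance of success from 91.8% to 86.3%, below the planned 90%. At 97% the loss is minor. For sensitivity, the primary endpoint, the effect is small: upward if missed cancers shed less than those found, downward if they shed more. A reader might infer that the primary result is inflated; the figures do not support that as a general statement.

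The plan should be amended, because the remedy is cheap and defines what both endpoints measure. Confidence in the practical size is moderate at best.

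**What to change.** Reconcile 5.1 with 7.1, and then:

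1. In 7.1 and 7.3, define disease status in both groups as the final recorded diagnosis for the index neck lump: histology from biopsy or excision where done, otherwise no HNSCC recorded within a fixed window after the baseline sample. Class participants with a non-diagnostic aspirate by the same rule.
2. Have the sponsor set the window before any ctDNA result is known. It should be short enough to reflect disease present at baseline, since the endpoints are defined there.
3. Assign status without knowledge of the ctDNA result.
4. Hold final diagnosis, its source and its date in the Data Tool, adding these only if absent, and build the 2x2 table from them.
5. State in 7.4 that the 49 and the 121 are counted by that status.

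**Cost.** One record look-up per participant and no extra procedure. The look-up runs across trusts and after the clinic visit, whereas 8.1 describes entry by the nurse in clinic, so it may need a minor amendment or a check that consent covers it. The last participants must be followed to the end of the window before analysis. Because status is settled after recruitment, final counts may differ slightly from 49 and 121, and the cut-offs would then need recalculating for the counts achieved. Diagnoses made elsewhere may still be missed, so misclassification is reduced, not removed.
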